7.2 PARTICIPANT DISCONTINUATION/WITHDRAWAL FROM THE STUDY

Participants are free to withdraw from participation in the trial at any time upon request. Participants who decide to withdraw will be reminded of the importance of completing their full course of definitive antimalarial treatment. The Principal Investigator will demonstrate due diligence in following up with the participant to ensure antimalarial therapy has been completed successfully.

The Investigator may discontinue or withdraw a participant from the trial for the following reasons:

- Pregnancy.
- Significant trial intervention non-compliance.
- If any clinical AE, laboratory abnormality, or other medical condition or situation occurs (or is revealed after previously being unknown) such that continued participation in the trial would not be in the best interest of the participant.
- The participant is not dosed with the IMP (see Section 7.1).
- Investigator discretion.

The Principal Investigator will ensure all withdrawn participants successfully complete the full course of definitive antimalarial treatment.

Participants who decide to withdraw, or are withdrawn, will be asked to complete an early termination visit (procedures for this visit will be the same as for the EOS visit). Any ongoing AEs present at the time of withdrawal/discontinuation will be followed-up by the Principal Investigator as specified in Section 8.3.5.

The Sponsor will be informed immediately of any withdrawals. The reason for participant discontinuation or withdrawal from the trial will be recorded in the eCRF.

Participants who withdraw, or are withdrawn or discontinued from the trial, may be replaced after mutual agreement between the Sponsor and the Principal Investigator. The decision regarding the replacement of participants will be documented.

7.3 LOST TO FOLLOW-UP

If a participant does not attend a scheduled visit, the Investigator will apply due diligence by documenting all steps taken to contact the participant (e.g., dates of phone calls, registered letter, home visit, etc.) in the source documents.

It will be explained to the participants during the consenting process and throughout the trial that they must be readily contactable. The period from inoculation to definitive antimalarial treatment is the critical period for participant safety. A participant will be deemed “missing” if they fail to reply to communication to their personal mobile phone and nominated contact’s number after 24 h. If after 36 h the participant fails to respond then the Investigator will organise a home visit. Subsequently, if the participant is still absent, the Investigator will request assistance from the local police to locate the missing participant. Once the participant is found, definitive antimalarial treatment will be administered.

A participant will be deemed lost to follow-up in the unlikely event that the participant is unable to be contacted or located despite all of the above measures. This is not anticipated to occur prior to administration of definitive antimalarial treatment, as in this situation, all efforts to locate the participant, including with assistance from local police, would continue until the participant is located and treated.

8 STUDY ASSESSMENTS AND PROCEDURES

The timing of each of the assessments described below is summarised in the SOA table (section 1.3) and the order of assessments at each visit is outlined in detail in the study conduct schedule (Appendix 12.1).

8.1 PHARMACOKINETIC AND PHARMACODYNAMIC ASSESSMENTS

8.1.1 PHARMACOKINETICS

Blood samples will be collected to quantify MMV367 plasma concentrations for PK analysis. Population PK modelling will be performed as part of the PK/PD analysis of MMV367 (primary endpoint). PK parameters of MMV367 will also be calculated using non-compartmental methods (secondary endpoint).

Samples will be analysed for MMV367 plasma concentrations using a validated analytical method in compliance with the SOPs of the laboratory performing the analyses. Assays will be performed in a Sponsor approved laboratory.

Plasma for MMV367 concentrations will be collected at the time points specified in the Schedule of Activities (Section 1.3). Allowed time windows for sample collection are as follows. The actual time of blood sampling will be recorded instead of the nominal time point.

Time point	Allowed time window
Inpatient observation pre-IMP (Day 8)	- 60 minutes
Inpatient observation \leq 16 hours post-IMP (Day 8)	\pm 15 minutes
Inpatient observation \geq 24 hours post-IMP until discharge (Days 9-11)	\pm 60 minutes
Outpatient monitoring (Day 12)	\pm 4 hours
Outpatient monitoring (Day 13)	\pm 12 hours
Outpatient monitoring Days 15-27	\pm 24 hours

8.1.2 PHARMACODYNAMICS

Blood samples will be collected to monitor malaria parasitaemia using polymerase chain reaction (malaria PCR). Total malaria parasitaemia will be quantified throughout the study by quantitative PCR targeting the gene encoding *P. falciparum* 18S rRNA (malaria 18S qPCR; reported as parasites/500uL packed RBCs). After discharge from the clinical trial unit, parasite lifecycle stages will also be determined by reverse transcriptase qPCR (qRT-PCR). The qRT-PCR assays will target the female gametocyte-specific transcript *pfs25*, the male gametocyte-specific transcript *pfMGET*, and the ring-stage transcript *pfSBP-1*.

Malaria PCR data will be used for the PK/PD analysis of MMV367 (primary endpoint) and to determine the kinetics of parasite clearance following MMV367 dosing (secondary endpoint).

Malaria PCR will also be used to guide the timing of definitive antimalarial treatment initiation. The requirement for Primacin® administration to clear gametocytes will be informed by the parasite lifecycle stage data.

Samples for malaria PCR will be analysed using validated analytical methods in compliance with the SOPs of the laboratory performing the analyses. Assays will be performed in a Sponsor approved laboratory.

Blood samples for malaria PCR will be collected at the time points specified in the SOA (Section 1.3). Allowed time windows for sample collection are as follows. The actual time of blood sampling will be recorded instead of the nominal time point.

Time point	Allowed time window
Pre-malaria inoculation (Day 0)	- 4 hours
Outpatient monitoring pre-IMP (Days 4-6)	± 12 hours
Outpatient monitoring pre-IMP (Day 7 AM)	± 4 hours
Inpatient observation pre-IMP (Day 8)	- 60 minutes
Inpatient observation ≤24 hours post-IMP (Days 8-9)	± 30 minutes
Inpatient observation >24 hours post-IMP until discharge (Days 9-11)	± 60 minutes
Outpatient monitoring (Day 12)	± 4 hours
Outpatient monitoring (Day 13)	± 12 hours
Outpatient monitoring Days 15-27)	± 24 hours

Additional samples may be collected at the discretion of the Investigator based on previous malaria PCR results and clinical symptoms. Following definitive antimalarial treatment, no further blood collection for malaria PCR is required for a participant once a minimum of one negative qPCR result is recorded.

8.2 SAFETY, ELIGIBILITY AND OTHER ASSESSMENTS

All safety assessments may be conducted at unscheduled visits or time points if required for the participant's safety at the discretion of the Investigator.

The following time windows will be allowed for vital signs recording, ECGs and blood sampling for clinical laboratory evaluations:

Time point	Allowed time window
Pre-malaria inoculation (Day 0)	- 4 hours
Outpatient monitoring pre-IMP (Days 4-6)	± 12 hours
Outpatient monitoring pre-IMP (Day 7 AM)	± 4 hours
Inpatient observation pre-IMP (Day 7 PM)	± 4 hours
Inpatient observation pre-IMP (Day 8)	- 2 hours
Inpatient observation ≤24 hours post-IMP (Days 8-9)	± 30 minutes
Inpatient observation >24 hours post-IMP until discharge (Days 9-11)	± 60 minutes
Outpatient monitoring (Day 12)	± 4 hours
Outpatient monitoring (Day 13)	± 12 hours
Outpatient monitoring from (Days 15-27)	± 24 hours

8.2.1 BECK DEPRESSION INVENTORY

Originally described by Beck et al (1961), the Beck Depression Inventory is a validated objective tool for the assessment of depression. Updated in 1996, the Beck Depression Inventory II (BDI-II) is a 21-item, self-report rating inventory that measures characteristic attitudes and symptoms of depression, and participants will be required to complete the BDI-II at Screening for eligibility. The BDI-II takes approximately 10 minutes to complete, although participants require a fifth – sixth grade reading level to adequately understand the questions. A score of >20 at screening and/or a response of 1, 2 or 3 for item 9 indicating current suicidal ideation is exclusionary. A participant with a BDI-II score of 17 to 19 may be enrolled at the discretion the Investigator if they do not have a history of the psychiatric conditions mentioned in exclusion criterion 10-12 and their mental state is not considered to pose additional risk to the health of the participant or to the execution of the trial and interpretation of the data gathered.

8.2.2 PHYSICAL EXAMINATION

A **full physical examination** includes the following:

Weight
Height (Screening only)
Review of systems excluding genitourinary examination and including the following:
Head, neck (including thyroid), ears, eyes, nose and throat
Heart/circulation
Chest
Lungs
Abdomen
Skin
Neurological exam

A Full physical examination will be performed at Screening and at EOS.

An **abbreviated physical examination** will include heart/circulation, chest, lungs, skin, and abdomen. An abbreviated physical examination will be performed prior to inoculation with the malaria challenge agent and prior to administration of the IMP on Day 8.

When the **symptom-directed physical examination** is performed, body systems will be reviewed only if clinically indicated.

8.2.3 VITAL SIGNS

At screening, vital signs will be measured after the volunteer has rested in the supine position for 5 minutes. SBP and DBP will be measured again after the volunteer has transitioned to a standing position for 3 minutes to assess postural hypotension (see Section 5.2, exclusion criterion 10).

At all other time-points vital signs will be measured after the participant has rested in the seated position for at least 5 min.

The normal ranges for vital signs after administration of the malaria challenge agent are:

Parameter	Range
Systolic blood pressure	90-140 mmHg
Diastolic blood pressure	50-90 mmHg
Heart rate	50-100 bpm
Temperature	35.0-37.5°C
Respiratory rate	10-25 breaths/min

8.2.4 MALARIA CLINICAL SCORE

The malaria clinical score gives an indication of the severity of the induced malaria infection in each participant. Fourteen signs/symptoms frequently associated with malaria are graded using a 4-point scale (absent 0; mild: 1; moderate: 2; severe: 3) and summed to generate a total malaria clinical score (maximum score possible is 42). Severity will be graded in accordance with the CTCAE Version 5.0 Published: November 27, 2017. Mild (1) equates to CTCAE grade 1, Moderate (2) equates to CTCAE grade 2 and Severe (3) equates to CTCAE grade 3. The criteria are shown in the table below.

Symptom or sign	Clinical Score/CTCAE grade			
	Absent (0)	Mild (1)	Moderate (2)	Severe (3)
	CTCAE 1	Mild pain	CTCAE 2	Moderate pain; limiting instrumental activities of daily living (ADL)
Headache				Severe pain; limiting self-care ADL
Myalgia		Mild pain	Moderate pain; limiting instrumental ADL	Severe pain; limiting self-care ADL
Arthralgia		Mild pain	Moderate pain; limiting instrumental ADL	Severe pain; limiting self-care ADL

Symptom or sign	Clinical Score/CTCAE grade			
Fatigue		Fatigue relieved by rest	Fatigue not relieved by rest; limiting instrumental ADL	Fatigue not relieved by rest; limiting self-care ADL
Malaise		Uneasiness or lack of well-being	Uneasiness or lack of well-being; limiting instrumental ADL	Uneasiness or lack of well-being limiting self-care ADL
Chills		Mild sensation of cold; shivering; chattering of teeth	Moderate tremor of the entire body; narcotics indicated	Severe or prolonged, not responsive to narcotics
Sweating/hot spells		Mild sweating/hot spells not affecting ADL	Moderate sweating/hot spells; narcotics indicated	Severe or prolonged, not responsive to narcotics
Reduced appetite		Loss of appetite without alteration in eating habits	Oral intake altered without significant weight loss or malnutrition; oral nutritional supplements indicated	Associated with significant weight loss or malnutrition (e.g. inadequate oral caloric and/or fluid intake); tube feeding or TPN indicated
Nausea		Loss of appetite without alteration in eating habits	Oral intake decreased without significant weight loss, dehydration or malnutrition	Inadequate oral caloric or fluid intake; tube feeding, TPN, or hospitalisation indicated
Vomiting		Intervention not indicated	Outpatient IV hydration; medical intervention indicated	Tube feeding, TPN, or hospitalisation indicated
Abdominal discomfort		Mild pain	Moderate pain; limiting instrumental ADL	Severe pain; limiting self-care ADL
Fever		38.0-38.9°C	≥39.0-39.9°C	≥40.0°C
Tachycardia		HR ≥100 Asymptomatic, intervention not indicated	HR ≥100 Symptomatic; non-urgent medical intervention indicated	HR ≥100; Urgent medical intervention indicated
Hypotension		SBP ≤80 Asymptomatic, intervention not indicated	SBP ≤80 Symptomatic; non-urgent medical intervention indicated	SBP ≤80; Urgent medical intervention indicated
Total Score				
Maximum 3 x 14 = 42				

8.2.5 ELECTROCARDIOGRAPHS

A 12-lead ECG will be recorded after the participant has rested supine for at least 5 min. ECG tracings will be retained and labelled as per standard procedures at the clinical trial unit and will be recorded in the eCRF. Any clinically significant findings will be documented as AEs. The Investigator will sign and date each ECG as evidence of their review. ECGs will be recorded in triplicate at the screening and prior to inoculation with the malaria challenge agent on Day 0.

The normal ECG ranges after administration of the malaria challenge agent are:

Parameter	Range
PR interval	≤210 msec
QRS	50–120 msec
QTcF	Males: ≤450 msec Females: ≤470 msec

8.2.6 DIARY CARDS

Participants will be provided with diary cards after malaria inoculation on Day 0 and instructed to record symptoms, details of self-administered take home definitive antimalarial medication and concomitant medications used during the study. Participants will also be provided with thermometers to record their temperature in the event of symptoms of fever. The diary cards will be reviewed at each outpatient visit and any information will be entered in the eCRF.

8.2.7 LABORATORY TESTS

The required pathology tube types, sample volumes, and laboratory processing procedures will be described in the Laboratory Manual. Samples will be collected in accordance with clinical trial unit SOPs.

The Investigator will document the clinical significance of all results falling outside of the normal reference ranges. Changes from baseline (malaria inoculation and/or IMP dosing) will also be considered. Clinically significant abnormal results will be documented as AEs and followed-up as specified in Section 8.3.5.

Additional reflex testing may be conducted by the local laboratory (as per their SOPs) if safety laboratory values for a participant fall outside of the normal range/parameters. Unscheduled testing may be performed at Investigator's discretion.

The parameters that will be measured are listed below.

8.2.7.1 HAEMATOLOGY

White cell count (WCC)
Neutrophils (NEUT)
Lymphocytes (LYM)
Monocytes (MON)
Eosinophils (EOS)

Basophils (BAS)
Mean cell volume (MCV)
Red cell count (RCC)
Haemoglobin (HGB)
Haematocrit (HCT)
Platelet count (PLAT)
Red cell distribution width (RDW)
Reticulocyte count (RETI)
Blood Group and Rh(D) tests (Screening only)

8.2.7.2 BIOCHEMISTRY

Sodium (NA)
Potassium (K)
Chloride (CL)
Bicarbonate (BICARB)
Calcium (CA)
Corrected calcium (CCA)
Magnesium (MAG)
Glucose (GLUC)
Urea
Creatinine (CREAT)
Estimated glomerular filtration rate (eGFR) – CKD Epi calculation
Albumin (ALB)
Globulin
Total protein
Total bilirubin (BILI)
Direct (conjugated) bilirubin (BILDIR)
Alkaline phosphatase (ALP)
Alanine aminotransferase (ALT)
Aspartate aminotransferase (AST)
Gamma-glutamyl transferase (GGT)
Lactate dehydrogenase (LDH)
Phosphate (PHOS)
C-Reactive Protein (CRP) (not required at Screening)
Cholesterol (Chol) (Screening only)
Triglycerides (Trig) (Screening only)
High density lipoprotein (HDL) (Screening only)
Low density lipoprotein (LDL) (Screening only)

8.2.7.3 VIRAL SCREEN

HIV 1/2 (anti-HIV1 and anti-HIV2 Ab)
Hepatitis B (HBsAg, anti-HBc [IgG + IgM if IgG is positive])
Hepatitis C (anti-HCV)

8.2.7.4 COAGULATION PROFILE

Prothrombin Time (PT)
Activated Partial Thromboplastin Time (APTT)
International Normalised Ratio (INR)

8.2.7.5 RED BLOOD CELL ALLOANTIBODIES

Screening for red blood cell alloantibodies will be performed at screening and at the EOS visit to investigate potential alloimmunization associated with administration of the malaria challenge agent.

8.2.7.6 GLUCOSE 6-PHOSPHATE DEHYDROGENASE (G6PD)

Quantitative G6PD testing performed at screening only for participant eligibility.

8.2.7.7 PREGNANCY TESTING

At screening, a serum β -hCG pregnancy test will be conducted for all female participants, and FSH levels will be tested in post-menopausal females (at least one year post-menopausal). At the eligibility confirmation visit, an additional serum β -hCG pregnancy test will be performed for WOCBP (WONCBP are defined in Section 5.1).

On Day 0 (pre-inoculation) and Day 7 PM, urine β -hCG pregnancy tests will be conducted for WOCBP. An additional serum β -hCG pregnancy test will also be conducted for WOCBP at the EOS visit.

If a participant is found to have a positive urine pregnancy test at any stage during the study, a confirmatory serum β -hCG will be performed. If confirmed positive, the participant will be administered definitive antimalarial treatment and will be discontinued from the study. Pregnancy-specific reporting procedures and follow-up are outlined in Section 8.3.9.

8.2.7.8 URINALYSIS

Urine will be tested by dipstick at the clinical trial unit. If there are any abnormalities (more than trace amounts for protein, blood, and leukocytes), the urine will be sent for formal laboratory urinalysis per the clinical trial unit standard procedure for microscopy, culture and sensitivity.

Glucose (GLUC)
Bilirubin (BILI)
Ketone (KETONES)
Specific gravity (SPGRAV)
Blood
pH
Protein (PROT)
Urobilinogen (UROBIL)
Nitrite
Leukocytes (WBC)
Microscopy, culture and sensitivity (formal laboratory analysis if required)

8.2.7.9 URINE DRUG SCREEN AND ALCOHOL BREATH TEST

The urine drug screen and alcohol breath test will be performed at clinical trial unit. If the result of a urine drug screen or alcohol breath test is positive, the participant will not be enrolled in the study (if testing positive on Day 0) or administered the IMP (if testing positive on Day 7 PM) unless there is an explanation acceptable to the Investigator (e.g., the participant has stated in advance that they consumed a prescription or over-the-counter product that contained the detected drug) and the participant has a negative urine drug screen on retest. The urine drug screen may be repeated if the participant denies usage of any of these agents and the test result is believed to be a false positive.

Urine drug screen:	
Amphetamines	Opiates
Methamphetamines	Phencyclidine
Barbiturates	Tetrahydrocannabinol (cannabis)
Benzodiazepines	Tricyclic antidepressants
Cocaine	
Methadone	
Alcohol breath test	

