18. Must not have had malaria exposure that is considered by the Principal Investigator or their delegate to be significant. This includes but is not limited to: history of having travelled to or lived (>2 weeks) in a malaria-endemic region during the past 12 months or planned travel to a malaria-endemic region during the course of the trial; history of having lived for >1 year in a malaria-endemic region in the past 10 years; history of having ever lived in a malaria-endemic region for more than 10 years inclusive. For endemic regions see <https://malariaatlas.org/explorer/#/>, Bali is not considered a malaria-endemic region.

Alcohol use and smoking

19. History or presence of alcohol abuse (regular alcohol consumption in males >21 units per week and females >14 units per week (1 unit = ½ pint beer, or a 25 mL shot of 40% spirit, 1.5 to 2 units = 125 mL glass of wine, depending on type), or drug habituation, or any prior intravenous usage of an illicit substance.
20. Any individual who currently smokes cigarettes on a daily basis (including e-cigarettes, vaping, and other nicotine use).

Blood donation

21. Blood product donation to any blood bank during the 8 weeks (whole blood) or 4 weeks (plasma and platelets) prior to admission in the clinical unit on Day 8.
22. Individual unwilling to defer blood donations for at least twelve months after the EOS visit.

Laboratory results

23. Haematology, biochemistry or urinalysis results at screening or at the eligibility visit (Day -1 to Day -3) that are outside of the standard clinically acceptable laboratory ranges (Appendix 12.2) or are considered clinically significant by the Principal Investigator.
24. Positive result for: hepatitis B surface antigen (HBs Ag), anti-hepatitis B core antibodies (anti-HBc Ab), anti-hepatitis C virus (anti-HCV) antibodies, anti-human immunodeficiency virus 1 and 2 antibodies (anti-HIV1 and anti-HIV2 Ab), COVID-19 by PCR at Screening or RAT on Day 0, red blood cell alloantibodies.
25. Positive urine drug test. Any drug listed in the urine drug screen unless there is an explanation acceptable to the Investigator (e.g., the participant has stated in advance that they consumed a prescription or over-the-counter product that contained the detected drug) and the participant has a negative urine drug screen on retest by the pathology laboratory.
26. G6PD deficiency (result below the lower limit of the laboratory reference range for quantitative G6PD test).

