7 STUDY INTERVENTION DISCONTINUATION AND PARTICIPANT DISCONTINUATION/WITHDRAWAL

7.1 DISCONTINUATION OF STUDY INTERVENTION

Once inoculated with the challenge agent on Day 0, it is expected that some study participants may experience mild to moderate malaria signs and symptoms prior to scheduled dosing with the IMP on Day 8. The following criteria should be considered as guidance for the decision not to proceed with administration of the IMP on Day 8 and to administer definitive antimalarial treatment instead:

1. A participant experiences an SAE or severe AE (\geq CTCAE Grade 3).
2. A participant returns a positive alcohol or urine drug screen.
3. A participant tests positive for SARS-CoV-2.
4. Investigator decision based on other safety signals (clinical, ECG, vitals and laboratory tests) not included in the above criteria if there is a perceived risk to participants.

In the event that definitive antimalarial treatment is initiated instead of dosing with the IMP, participants will be administered their first dose of antimalarial medication at the clinic (except in the event a participant tests positive to COVID-19; See Section 8.2.6.11 for details of COVID-19 management plan) but will then be able to return home. The participant will be contacted daily via phone to check that each dose of antimalarial treatment is being taken, and to ascertain any AEs. Following antimalarial treatment, blood will be taken for malaria PCR until at least one negative result is obtained. The participant will then be withdrawn from the study (see Section 7.2).

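### As written, section 8.2.7.9 lets a positive Day 7 PM alcohol breath test be cleared for dosing by a urine drug screen that does not measure alcohol

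*Protocol*

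**What the plan says.** Protocol section 8.2.7.9 covers both tests in one sentence. It begins: "If the result of a urine drug screen or alcohol breath test is positive, the participant will not be enrolled in the study" (the Day 0 case). It goes on to the Day 7 PM case: "or administered the IMP (if testing positive on Day 7 PM) unless there is an explanation acceptable to the Investigator". A second condition is joined to the first: "and the participant has a negative urine drug screen on retest". The section also allows the urine screen to be repeated if a false positive is suspected. It says nothing about repeating the breath test.

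Other sections bear on the same decision:

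- **Section 5.2, criterion 25** has the same exception for a positive urine drug test only, ending "and the participant has a negative urine drug screen on retest by the pathology laboratory".
- **Section 5.2, criterion 27** excludes a volunteer with a positive alcohol breath test and has no exception.
- **Section 7.1** introduces its list with "The following criteria should be considered as guidance for the decision not to proceed with administration of the IMP on Day 8". Item 2 reads: "A participant returns a positive alcohol or urine drug screen". No exception is attached to it.
- **Sections 8.2 and 8.2.7** permit extra testing: "All safety assessments may be conducted at unscheduled visits or time points if required for the participant's safety at the discretion of the Investigator", and "Unscheduled testing may be performed at Investigator's discretion".
- **The schedule of activities (1.3) and section 12.1.5** place a breath test at admission on Day 7 PM. Neither lists one among the Day 8 pre-dose procedures.

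**The concern.** A rule that releases a participant for dosing should rest on a test of whatever triggered the hold. Here a positive breath test can trigger the hold, and the only retest named is a urine drug screen. A participant who had been drinking could return a clean urine screen, meet that condition, and still have alcohol present.

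The situation is foreseeable. Section 5.3 allows up to 2 standard drinks a day outside confinement, and confinement begins on Day 7 PM. A participant could therefore drink within the rules, test positive at admission and offer an explanation that the Investigator finds acceptable.

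The stake is a dosing decision for someone already inoculated. Either the IMP is given, or definitive antimalarial treatment is given instead and the participant is withdrawn (7.1). Section 2.2.1 names alcohol as possibly hepatotoxic, in a challenge model with known transient liver enzyme elevations. No endpoint, analysis set or sample size depends on the rule.

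**Working it through.** The plan states no figure on this point. The check is a count and a comparison of sections.

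**1. What triggers the rule.** Section 8.2.7.9 names two triggers, a positive urine screen or a positive breath test. They share one consequence and one exception. Grammatically, the exception applies to both.

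**2. What the release test measures.** The urine panel in the same section lists:

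- amphetamines, methamphetamines, barbiturates, benzodiazepines, cocaine and methadone (6 classes);
- opiates, phencyclidine, tetrahydrocannabinol and tricyclic antidepressants (4 classes).

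6 + 4 = 10 classes, of which 0 are alcohol. The breath test has its own row. A negative urine retest therefore carries no information about alcohol.

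**3. Whether another rule closes the gap.**

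| Place | What it does | Day 0 | Day 7 PM |
|---|---|---|---|
| 5.2, criterion 27 | Excludes on a positive breath test, no exception | Closes it | Concerns enrolment only; the participant is already enrolled |
| 5.4 and 12.1.3 | Bar enrolment of anyone meeting an exclusion criterion; eligibility is checked before inoculation | Close it | Do not apply |
| 7.1, item 2 | Lists a positive alcohol screen as a reason not to dose | Does not apply | Points against dosing, but as guidance |
| 8.2 and 8.2.7 | Permit unscheduled tests at discretion | Permit | Permit a breath retest, do not require one |
| 1.3 and 12.1.5 | Schedule the breath tests | Test scheduled | Test scheduled at admission; 0 between then and dosing |

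On Day 0 the effect is only a wording mismatch with criterion 27. On Day 7 PM nothing binding removes the exception.

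**4. What the authors probably meant.** Criterion 25 uses the same clause for urine alone. The example in 8.2.7.9 speaks of a prescription or over-the-counter product containing the drug found, which fits a urine result and not a breath result. The likeliest explanation is that the clause was carried over from criterion 25 into a sentence that also mentions the breath test.

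**5. How many participants the rule can reach.** Up to 18 participants are planned, so up to 18 Day 7 PM admissions before any replacements. The documents give no rate of positive breath tests, so no expected number of cases can be derived from them.

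**6. What limits the harm.** Alcohol is barred during confinement (5.3), and only water is allowed for at least 8 hours before dosing (12.1.5). Any alcohol present at admission would therefore have at least 8 hours to fall. The documents name no interaction between MMV367 and alcohol.

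**The case against.** The strongest reply is that no sensible reader would apply the exception to alcohol. Its example and its retest both concern urine drugs, a participant positive only on breath has no positive urine result to retest, and criteria 25 and 27 keep the two tests apart. This is persuasive about intent, and it is why the point is graded as a probable slip. It does not make the text sound. The example is introduced as an example, not as a limit. On the narrower reading, 8.2.7.9 forbids dosing outright after a positive breath test, while 7.1 treats the same result as guidance. The sections disagree either way.

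A second reply is that if 7.1 is guidance, the Investigator already has discretion over dosing and can repeat the breath test. That is true, so a reader should not infer that a repeat is unavailable. It is optional, while the one retest that 8.2.7.9 makes a condition is uninformative about alcohol.

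A third reply is that the protocol does not treat alcohol near MMV367 exposure as a specific hazard. Participants may resume up to 2 drinks a day after discharge on Day 11. That is 72 h after dosing, or 72 / 17 = 4.2 of the half-lives given in section 4.2, when some drug remains. This stands, and it keeps the safety concern very small.

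A reader might also infer that the sponsor chose to let participants be dosed with alcohol present, or that the slip opens enrolment on Day 0. The documents support neither. Criterion 25 points to misdrafting and not to a choice, and criterion 27 with 5.4 and 12.1.3 already bars enrolment.

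**Conclusion.** The point holds as a minor wording inconsistency in an operative dosing rule. For a positive breath test on Day 7 PM, the stated release condition cannot show that alcohol has cleared: 0 of the 10 urine classes detect it, and 0 repeat breath tests are required before dosing. The conclusion rests on the literal grammar of 8.2.7.9 and on the express status of the 7.1 criteria as guidance. It does not assume that any site would apply the exception this way.

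The practical risk is very small. Harm would need a positive test, an accepted explanation despite 7.1, a negative urine retest, no discretionary breath repeat, and alcohol still present after confinement and the fast. A reader might infer a material threat to participant safety or to the trial's results. The documents do not support that: they name no MMV367-alcohol interaction, and no endpoint, analysis set or sample size is touched.

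**What to change.** Three changes to the protocol wording:

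1. In 8.2.7.9, limit the exception (accepted explanation plus negative urine retest) to positive urine drug screens, as criterion 25 does.
2. In 8.2.7.9, state that after a positive breath test on Day 7 PM the IMP is not given unless a repeat breath test before dosing is negative.
3. Align 7.1 item 2 with that rule. Otherwise it would still list the first positive result as a reason not to dose someone whom 8.2.7.9 has released.

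The cost is a short wording amendment and an occasional repeat breath test during confinement, with no new visit. A participant who drank within the permitted limit can still be dosed once the repeat is negative. If the repeat stays positive, one dose is withheld, out of up to 6 in a cohort. Randomisation follows on Day 8, its schedule already allows for withdrawals before dosing (6.3), and replacement is possible under 7.2.
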